### **General Information**

This document describes the data collection study and provides information about procedures for entering patients into it. The protocol should not be used as an aide-memoire or guide for the treatment of other patients; every care was taken in its drafting, but corrections or amendments may be necessary. Clinical problems relating to this study should be referred to the Chief Investigator.

### **Compliance**

The study will be conducted in compliance with the protocol, GCP, GDPR, NHS research governance, the Declaration of Helsinki, and the terms of the favourable opinion from the National Research Ethics Service.

### **Funder**

Funding will be from Edwards Lifesciences Ltd

## 1. Background

The brain has a high metabolic demand and receives about 12% of cardiac output (CO) (1). This high metabolic demand makes the brain at risk for injury when disturbances in hemodynamic status occur, e.g. during surgery. However, cerebral autoregulation is responsible for protecting the brain from injury caused by hemodynamic changes (2,3). The concept of cerebral autoregulation, including a lower limit, a plateau and an upper limit, was proposed in 1959 (4), which means that when cerebral perfusion pressure (CPP) is in the range between 50 and 150 mmHg cerebral blood flow (CBF), and hence oxygen delivery remains more or less constant by adjusting vascular resistance (3). A combination of myogenic, neurogenic, metabolic, and endothelial mechanisms are responsible for maintaining cerebral autoregulation (3). In case of an increase in CPP, local vasoconstriction occurs and in case of a decrease in CPP, vasodilatation occurs to maintain constant CBF. Cerebral perfusion pressure is calculated as mean arterial pressure (MAP) minus intracranial pressure and central venous pressure, and can be substituted by MAP when no elevation in intracranial pressure is suspected (5). When CPP or MAP reach values outside of the autoregulation range, CBF will become directly dependant on blood pressure resulting in decreased CBF and hence oxygen delivery which may result in postoperative neurologic complications.

Cerebral oxygenation as a surrogate of CBF in the assessment of cerebral autoregulation (5), can be measured by near-infrared spectroscopy (NIRS) and is increasingly used in the routine clinical care as cerebral oxygenation values have been associated with postoperative neurologic and general complications (6). The ForeSight Elite sensor technology allows for effective tissue interrogation by incorporating 5 wavelengths of near-infrared light to analyse tissue, providing a broad spectrum of NIRS wavelengths (685, 730, 770, 810, 870nm). This allows for effective tissue interrogation at points where oxygenated and deoxygenated haemoglobin are more greatly distinguished for highly accurate performance. The sensors are non-invasive and placed on the forehead and can measure tissue oxygenation to a depth of 2.5cm.

Using blood pressure measurements and by examining changes in cerebral oxygenation autoregulation curves can be created as well as upper and lower limits of autoregulation as has been previously performed (7–10). The trend in

hemodynamic monitoring however is to progressively use less invasive monitoring tools.

The ClearSight™ non-invasive hemodynamic monitoring technology measures blood pressure using the volume clamp method developed by the Czech physiologist Jan Penaz (11,12). Using a simple non-invasive finger cuff, the volume of an artery is kept clamped at a constant diameter. Changes in diameter are measured by a photo-plethysmograph within the finger cuff, and a servo controller applies counter pressure to keep the diameter of the artery constant. This allows the measurement of beat to beat blood pressure and with additional algorithms cardiac output can also be calculated. The simple and non-invasive nature of this device makes it suitable to use in patients undergoing repair of fractured neck of femur regardless of the type of anaesthetic. It requires no calibration, and would make goal directed therapy accessible to this group. The ClearSight has been shown to be a valid measure of cardiac output and blood pressure(13).

A recent meta-analysis showed that several studies found invasive blood pressure monitoring interchangeable with finger cuff technologies, however the pooled results showed the contrary and that both were not interchangeable in surgical or critically ill patients (14). Hence autoregulation limits mapped by invasive blood pressure monitoring may not reflect those mapped by this less invasive technology.

The kidneys also have an autoregulation system to protect themselves from disturbances in hemodynamic status (15). Similar to the brain, in case of an increase in renal perfusion pressure (RPP), vasoconstriction occurs and in case of a decrease in RPP, vasodilatation occurs to maintain constant renal blood flow (RBF). The two mechanisms responsible for renal autoregulation are the myogenic response and the macula densa tubuloglomerular feedback (MD-TGF) response (16). The concept of an upper and lower limit also applies to renal autoregulation.

## 2. Rationale and Aim

The aim of this study is to acquire data that will allow to create cerebral and renal autoregulation curves and assess the agreement between invasive and non-invasive blood pressure measurements in patients undergoing elective surgery requiring continuous invasive hemodynamic monitoring. Blood pressure measurements will be

obtained invasively with an arterial catheter and non-invasively with the ClearSight sensor applied to one of the fingers, whilst cerebral and renal oxygenation is measured by NIRS. The data collected will also be used to help develop predictive algorithms for cerebral desaturation.

## **2.1 Risks and benefits.**

There are no additional benefits for individuals taking part in this study

As with all optical sensors (ForeSight), there is the theoretical risk of thermal burn. The design includes safeguards, and this risk is believed to be minimal. Sensors will be attached with adhesive and may be secured by a supplemental headband. Optical exposure is minimized by procedure and low power. Overall risk is estimated to be low for the ForeSight sensors and site check are performed on a regular basis. Additionally, the ClearSight sensors could theoretically pressure damage if placed too tightly, however this risk is also estimated as low, and no reported cases have been described.

## **3. Study Sites**

This study will take place in the surgical unit, operating theatres and post anaesthetic care unit, York Hospital, [name], and the surgical unit, operating theatres and post anaesthetic care unit of the University Medical Centre Groningen, [name], The Netherlands.

## **4. Selection of Patients**

### **4.1 Patient inclusion criteria.**

Patients due to undergo elective major non-cardiac surgery requiring invasive arterial monitoring (decided at the discretion of the treating clinician) under general anaesthesia, and with an expected duration of greater than 90 minutes,

### **4.2 Patient exclusion criteria**

A potential subject who meets any of the following criteria will be excluded from participation in this study:

- Subject has skin abnormalities affecting the forehead, flank or skin of the upper leg that would prevent monitoring of tissue oxygenation during the study
- Patients undergoing cardiac surgery with cardiopulmonary bypass (non-pulsatile blood flow)
- Age < 18 years

### **4.3 Number and source of patients and participants .**

100 patients undergoing major non cardiac surgery will be recruited – 50 from each participating site.

### **4.4 Identification, recruitment and consent.**

The identification and consent process is described below, and only patients with capacity will be recruited

Patients scheduled for major elective surgery that meet the inclusion criteria will be given the Patient Information Leaflet at the earliest opportunity. Patient Information Leaflets will be posted to potential participants with their pre-operative assessment information, or alternatively given out by one of the researchers or research nurses at the pre-operative assessment clinic. During normal working hours, a member of the research team will be available to answer any questions relating to the research project. All members of the research team will have an in-depth knowledge of the protocol and all have been involved in various research projects using this technology. Once the Patient Information Leaflet has been given out, a sticker will be placed in the clinical notes stating that the patient is eligible for the study and has been given the information. This sticker will be timed and dated. Those patients eligible to take part will be asked to consent having had time to consider the proposal. Consent will be received either by the Chief Investigator, the Co-Investigators or an appropriately trained Research Nurse, and will normally take place at either the pre-operative assessment clinic or on admission to hospital depending on when the individual received the patient information sheet. Another sticker will be placed in the notes stating that informed consent has been received. Again, this will be timed and dated. Three copies of the consent form will be taken –

the original for the site file, one copy for the patient and one to go into the patient's notes.

If people withdraw from the study, data collected until the point of withdrawal will be included in the study.

#### **4.5 Screening procedures and pre-randomisation investigations.**

Electronic theatre lists will be screened to find patient subjects eligible for the study. This is the only screening procedure. No other investigations are necessary for the conduct of this study. Patients will receive their standard pre-operative work-up, irrespective of whether they participate in the study or not. A decision to withdraw, or a decision not to take part will not affect the standard of care that the patient receives.

## **5. Allocation**

### **5.1 Allocation to treatment**

This will be a prospective non randomised observational study recruiting 50 sequential patients at both sites. There is no allocation to treatment and all subjects will receive standard institutional care.

### **5.2 Co-enrolment guidelines.**

For the duration of their involvement in this study, patients may be co-enrolled in other perioperative studies as long there is no intervention performed during the intraoperative period. This would include observational studies and interventional studies where the intervention is performed after recovery from anaesthesia.

## **6. Treatment of Patient Participants**

When the participant arrives in the operating room they will be connected to standard monitoring including non-invasive blood pressure, ECG and SpO2. An arterial cannula (standard care) will be placed in a radial artery (brachial artery if radial is

unable to be cannulated) under local anaesthesia and connected to a FloTrac IQ transducer and haemodynamic data will be displayed on the Hemosphere platform. This monitor will be designated monitor 1. Subsequently, all study sensors will be applied. A Foresight sensor will be placed on the flank, above the kidney (localised by ultrasound) and one on the skin above the quadriceps, at a muscle dense location. Two sensors will be applied to the forehead and will be secured with a headband if necessary. The Foresight sensors will also be connected to the Hemosphere monitor 1. A ClearSight cuff will be placed on a suitable finger on the ipsilateral hand and connected to a second Hemosphere monitor, designated monitor 2. Both monitors will be synchronised for date and time.

A period of ten minutes will be used to capture baseline data before anaesthesia is induced. All treatment will be as per standard institutional care and none of the sensors will be used to guide treatment, except for the FloTrac sensor, which will be used according to routine clinical practice.

All interventions during the procedure including but not limited to fluid therapy, vasoactive drug administration and positional changes will be entered on to the hemosphere platform (monitor 1), and at the end of surgery, all data will be downloaded from each Hemosphere monitor.

Monitor 1 will provide measurements of cardiac output, cardiac index, stroke volume variation, stroke volume, stroke volume index, hypotension probability index, pulse rate, and systolic, diastolic and mean arterial pressure from the invasive arterial waveform and cerebral, renal and muscle tissue oxygen saturations.

Monitor 2 will provide measurements of cardiac output, cardiac index, stroke volume variation, stroke volume, stroke volume index, hypotension probability index, pulse rate, and systolic, diastolic and mean arterial pressure from the non-invasive arterial waveform.

Anonymised versions of all raw waveform data and EMR data will be sent to Edwards Lifesciences for further analyses, including computation of  $dP/dT$ , Eadyn and PPV, and development of predictive algorithms for mapping cerebral desaturations and autoregulation curves from the raw data. Patients' consent for this data transfer to Edwards Lifesciences and outside the EU is obtained as part of the consent process.

### **6.1 Anaesthetic technique.**

Anaesthetic technique will be at the discretion of the anaesthetist as per the current practice at the host institution.

### **6.2 Discontinuation criteria.**

Patients will be withdrawn from the trial

1. Voluntary withdrawal (by patient or consultee).

If subjects are withdrawn from the trial, data collected up to that point will be retained.

If the duration of planned surgery is less than the inclusion criteria then an additional subject will be recruited.

### **6.3 Withdrawal of patients.**

In consenting to the trial, patients are consenting to data collection. If a patient wishes to withdraw from the trial prior to surgery they shall be free to do so with no detriment to their medical care

### **6.4 Blinding.**

There is no blinding as this is an observational non interventional study.

## **7. Regulatory issues.**

A notice of no objection from the MHRA is not necessary as the Hemosphere monitor, FloTrac IQ sensor, ClearSight system and Foresight NIRS sensor are all CE marked medical devices being used for their intended purpose. The study also does not require a Clinical Trial Authorisation from the MHRA as it is not a Clinical Trial of an Investigational Medicinal Product.

## **8. Assessments**

### **8.1 Chart for pre and intra-operative data.**

See Case Record File.

## **8.2 Loss to follow-up.**

It is highly unlikely that there will be any loss to follow up as data collection ceases at the end of surgery.

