### 13.1 Definition of Adverse Events/Reactions

#### Adverse Event (AE)

An adverse event is defined as any untoward medical occurrence that occurs to a study participant during the course of the study. Information about adverse events will be collected from the beginning of any study related procedure. For the purpose of this study this is defined as the induction of anaesthesia

For the purpose of this study the adverse events that will be recorded are those that may occur as a result of the sensors applied. Such adverse events will include, but will not be limited to:

- Thermal burns
- Digit ischaemia or injury
- Pain at sensor sites
- Reaction whether due to allergy or otherwise to the sensors
- Any other adverse event deemed relevant by the Chief Investigator.

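### Sensor-site pain is collected only while the patient is anaesthetised, delayed digit injury has no scheduled check, and Sections 8.2 and 8.3 conflict with 13.3 and 13.4 on when safety observation ends

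*Protocol*

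**What the plan says.** - **What is to be recorded.** Section 13.1 confines recorded adverse events to those the applied sensors may cause. The list includes "Digit ischaemia or injury" and "Pain at sensor sites", with thermal burns, sensor reactions and a catch-all item.
- **When collection starts.** Section 13.1 ties the start to the first study procedure and then defines that moment as induction.
- **When it stops.** Section 8.2, explaining why loss to follow-up is unlikely, states that "data collection ceases at the end of surgery". Section 8.3 ends the study when the last patient's operation is complete.
- **What happens to events.** Section 13.3 follows adverse events until discharge or Day 10, whichever is earlier. Section 13.4 follows serious events to their conclusion, by telephone or an extra visit if needed.
- **Exposure.** Section 6 applies all sensors before a ten-minute baseline in the awake patient. For the cuff: "A ClearSight cuff will be placed on a suitable finger on the ipsilateral hand", that is, on the side of the arterial cannula.
- **Stated checks.** Section 2.1: "Overall risk is estimated to be low for the ForeSight sensors and site check are performed on a regular basis". The next sentence says that "the ClearSight sensors could theoretically pressure damage if placed too tightly", rates that risk as low, and attaches no check to it. Section 6 does not mention site checks.

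**The concern.** Pain is known only if an awake patient reports it. Pressure or ischaemic injury to a finger can be seen by staff, but may show itself only after the cuff is off. If the collection window runs from induction to the end of surgery, it nearly coincides with the period of unconsciousness. A report of no sensor-site pain would then say little about whether pain occurred, because no patient was asked at a time when an answer was possible. A finger injury noticed later on the ward would have no recorded finding at cuff removal against which to date it. Two sites could also read the end of safety observation differently, one following 8.2 and the other 13.3, and so collect different safety data in the same study.

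**Working it through.** No arithmetic applies. The check is to set the stages of a participant's stay against what the protocol provides at each.

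| Stage | Patient can report? | Sensors on? | Adverse event collection as written | Scheduled look at the finger |
|---|---|---|---|---|
| Sensor application and ten-minute baseline (Section 6) | Yes | Yes | Not yet open (13.1 starts at induction) | None stated |
| Induction to end of surgery (4.1, 6) | No | Yes | Open | None stated; 2.1 gives checks for ForeSight only |
| After surgery, post anaesthetic care unit (Section 3) | Yes, once awake | Removal time not stated | Closed if 8.2 is taken literally; no closing time in 13.1 | None stated |
| To discharge or Day 10 (13.3) | Yes | No | Follow-up of events; no search for new ones described | None stated |
| Beyond (13.4) | Yes | No | Follow-up of serious events to conclusion | None stated |

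Four things follow.

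1. **Pain.** On the literal reading, the one stage at which collection is plainly open is the one at which the patient cannot speak. The awake baseline does not help: a complaint of cuff pain during it falls before the window opens. Section 13.1 is also at odds with Section 6 here, since applying the sensors is itself a study procedure and precedes induction.

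2. **Digit injury.** Staff can see this during surgery, so it is not lost in the same way as pain. The gap is for injury that becomes apparent after the operation: no section schedules an inspection at cuff removal or after waking.

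3. **End of observation.** Sections 8.2 and 8.3 put the end at surgery; 13.3 and 13.4 run past it. For the last patient, any follow-up under 13.3 would fall after the study has ended by the definition in 8.3. Sections 13.3 and 13.4 set how long an event is followed, not how it is found, so they do not supply the missing ascertainment.

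4. **Site checks.** The sentence on regular checks has the ForeSight sensors as its subject and gives no interval. The cuff risk follows in the next sentence without a check. Whether the finger is included cannot be settled from the text.

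**The case against.** The strongest reply is that 8.2 is not a safety provision. It explains why study data will be complete, while Section 13 governs safety, gives no stop at the end of surgery, and keeps the research team in touch with patients who have had an event. An awake patient could volunteer a complaint and it might well be recorded. The case record file (8.1) and the sponsor's adverse event procedures (Section 13) are not shown and may contain a check. The study is observational, uses CE-marked devices for their intended purpose (Section 7), and has no safety outcome in Section 9.1.

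Much of this stands, and it rules out some stronger readings:

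- A reader might infer that nobody looks for harm after surgery. The documents do not support that; 13.3 and 13.4 continue past it. What is missing is a scheduled look.
- A reader might infer that patients never have a chance to report while wearing the sensors. They do, during the awake baseline; the fault is that the window is not yet open.
- A reader might take the exclusion for "skin abnormalities affecting the forehead, flank or skin of the upper leg" as a safeguard that forgot the hand. Section 4.2 gives its purpose as making tissue oximetry feasible. The finger cuff measures blood pressure, so omitting the hand is consistent with that purpose, and no change to eligibility follows.
- A reader might try to put a number on the gap from wearing time, nurse hours or a bound on the event rate. The protocol gives expected rather than actual duration, does not say that the nurse attends throughout, and claims no event rate.

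What the reply does not remove is the contradiction in the text. Even if the case record file holds a post-operative check, 8.2 as worded conflicts with it.

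**Conclusion.** The point holds as a defect in safety ascertainment, with a contradiction between sections. It is complete for sensor-site pain on the literal reading of 8.2 and 13.1, and partial for digit injury, where only delayed injury escapes. It applies to every one of the 100 planned patients. It does not touch the autoregulation curves, the agreement analyses or the algorithm development, so it merits correction without calling the design into question. The conclusion assumes that 8.2 means what it says and that the case record file and sponsor procedures add no scheduled check. If they do add one, what remains is the need to reconcile 8.2 and 8.3 with 13.3 and 13.4, to align the start in 13.1 with Section 6, and to say whether site checks cover the finger.

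**What to change.** 1. In 8.2 and 8.3, limit the end-of-surgery statements to waveform and intra-operative data, and make both consistent with the follow-up periods in 13.3 and 13.4.
2. In 13.1, open adverse event collection at sensor application instead of induction, so that the awake baseline is covered.
3. In 2.1 and Section 6, state that site checks include the cuffed finger.
4. In Section 6 and the case record form, add one recorded inspection of all sensor sites at sensor removal, and one question-and-look check after recovery from anaesthesia. The post anaesthetic care unit is already a study location under Section 3, so no extra appointment is needed and the assurance on appointments in 12.1 is kept.

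The cost is a few sentences of protocol text, two case record form lines, and a few minutes of existing staff time per patient. One limit remains: because the cuff and the cannula are on the same side, an inspection will date a finger injury but will not by itself separate a cuff effect from a cannula effect.

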## **8.3 Trial closure.**

The study shall end when the last patient has been has completed surgery.

At the point of study closure the Chief Investigator shall notify the Sponsor in writing that the study has ended. This shall be done in accordance with the York Teaching Hospitals NHS Foundation Trust R and D unit SOP on Trial Closure. Study data will be archived in accordance with the York Teaching Hospitals NHS Foundation Trust and University Medical Centre Groningen SOP

